The objective of this pilot study is to evaluate the feasibility and compare the potential effect of different vaping cessation intervention components in addition to evidence-based text-messaging support, including 1) media literacy interactive e-learning lessons, 2) financial incentives, and 3) combined (media literacy + financial incentive) on vaping abstinence among current young adult vapers over a three-month timeframe with the following three specific aims: Aim 1. To assess the feasibility of a multi-component vaping cessation program; Aim 2 To evaluate the preliminary effect of a multicomponent vaping cessation program; and exploratory Aim 3. To Examine the cost-consequence of a multicomponent vaping cessation program. Eligible participants are young adults aged 19-29 and are current vapers (i.e., using e-cigarettes in the past 30 days). We will employ a 4-arm, feasibility randomized trial design to determine the preliminary effect of different vaping intervention components on vaping abstinence over a 3-month timeframe, consisting of a 1-month quitting preparation phase and 2-month abstinence phase. Eligible participants (n=80) will be randomized (in a 1:1:1:1 ratio), using a computer-generated algorithm, to one of four vaping cessation interventions: 1) Active control: text-messaging support, 2) Media literacy: media literacy + text-messaging support, 3) Financial incentive: financial incentive + text-messaging support, and 4) Combined: media literacy e-learning lessons + financial incentive + text-messaging support, at the baseline visit. Regardless of intervention arms, all enrolled participants will receive an evidence-base text-messaging support program for quitting vaping (This is Quitting). Participants will be followed through a 3-month study period including a 1-month quitting preparation phase and a 2-month abstinence phase. All participants will be asked to provide 5 saliva cotinine samples- at baseline and end-of-study visits and 3 at video calls (remote submissions). Participants who assigned to the financial incentive Combined groups will be provided monetary rewards for submitting saliva cotinine samples during the abstinence period. To examine the feasibility of biomarker testing for toxic exposures, for a subsample of 20 participants, a panel of biomarkers of toxic exposures will be measured at baseline and at the end of study.

PURPOSE OF THE STUDY AND BACKGROUND

2. Purpose of the Study

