Contingency management is an established behavioral intervention in which individuals receive reinforcement (e.g., financial incentives) contingent upon biochemically verified abstinence.¹¹ Incentives have been used to encourage healthy behaviors,¹² and as an implementation strategy to improve EBP reach and engagement.¹³ Moreover, social support has been integrated into smoking interventions to promote cessation.¹⁴ Notably, family and friend use is one of the top reasons for youth to use e-cigarettes¹⁵, and vaping for entertainment is common among young vapers.¹⁶ Studies have shown that peer support can be an effective strategy in increasing social support and promoting abstinence in smoking cessation, especially among young people.^{17,18} Although there is clear evidence that social support and financial incentives individually improve smoking cessation rates in mixed population,¹⁹ little is known regarding their individual and collective effect on vaping cessation program reach and effectiveness, especially targeting the young adult population.^{10,20}

CHARACTERISTICS OF THE SUBJECT POPULATION

4. Accrual

A. Is this study conducted solely at sites under the oversight of the UNMC IRB (e.g.

UNMC, Nebraska Medicine, CHMC, UNO)?

Yes

1. How many subjects will need to be consented (per group, as applicable) in order to achieve the scientific objectives of the research?

We will recruit 80 young adult current vapers aged 19-29 to test a four-arm pilot trial (*Active control, Media literacy, Financial incentive, and Combined*) with n=20 for each arm.

2. What is the statistical or other justification for the total number of subjects described above?

As this is a pilot feasibility study, and as the rule of thumb, it was suggested that a minimum sample size of 12 subjects per treatment arm or a total sample size of 70 in order to reduce the imprecision around the estimate of the standard deviation for a pilot trial. Accordingly, the sample size of 80 for this study would be sufficient to assess the preliminary effectiveness of financial and social incentives as well as determine the feasibility and ability to scale interventions to a larger group.

3. How long do you estimate it will take to accrue the required number of subjects?

We estimate that it will take about 3-4 months to accrue the required number of subjects.

5. Gender of the Subjects

A. Are there any enrollment restrictions based on gender?

No

6. Age Range of Subjects

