As this is a incentive-based (financial and social) enhanced vaping cessation study, there will not be therapeutic interventions or treatments other than educational lessons and support programs. Breastfeeding should not be impacted.

METHODS AND PROCEDURES

12. Methods and Procedures Applied to Human Subjects

A. Are there any evaluations or tests that will be performed for the purpose of determining subject eligibility which would not be routinely conducted as part of standard clinical care of the prospective subject?

Yes

1. Describe the evaluations or tests to determine subject eligibility

Interested potential participants will complete an online screen survey (RedCap link embedded in the recruitment email), to determine their eligibility based on the inclusion and exclusion criteria.

2. Are any of these evaluations or tests performed prior to obtaining informed consent?

Yes

B. Describe the research plan, including all procedures, interventions, evaluations and tests.

Study design

This study employs a pilot, 4-arm randomized clinical trial (RCT) design. Individuals who meet the eligibility criteria will be randomized (1:1:1:1) to receive one of the following interventions with a 1-month quitting preparation phase and a 2-month abstinence phase:

1) Active control-

Participants in this arm will receive an evidence-based text-messaging support

2) Media literacy-

Participants will receive media literacy e-learning lessons and an evidence-based text-messaging support

3) Financial incentive-

Participants will receive financial incentive intervention and an evidence-based text-messaging support

4) Combined-

Participants will receive media literacy e-learning lessons, financial incentive, and an evidence-based text-messaging support program

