2. Baseline and end-of-study survey, including demographic, vaping history, vaping experience/behavior, attempt to quit, Penn State Nicotine Dependence Index, exposure to Tobacco Marketing and Marketing Influences, UPPS impulsive behavior scale, money choice question, and self-efficacy about not to vape, and wheezing and related respiratory symptoms

Primary outcome

- **biochemically verified vaping abstinence** (negative results- will be cut-off < 30 ng/mL⁷¹), measured by saliva cotinine samples at the Week 12 visit.

Secondary outcome

1. Nicotine abstinence: bi-weekly/monthly saliva nicotine abstinence results (positive vs. negative) will be obtained using the iScreen test kit ([https://stat-technologies.com/product/alere-iscreen-for-cotinine/#:~:text=The%20Alere%20iScreen%C2%AE%20OFD,nicotine\)%20in%20human%20oral%20fluid.](https://stat-technologies.com/product/alere-iscreen-for-cotinine/#:~:text=The%20Alere%20iScreen%C2%AE%20OFD,nicotine)%20in%20human%20oral%20fluid.)) after the target quit date for 2 month in addition to baseline and Week 12 saliva cotinine samples. Saliva sample/results will be collect in person at baseline and Week 12 visits and remotely via live video calls during the abstinence phase. The remote saliva sample collection will follow the instruction below:

- Participants will open the new, labeled packaging for each testing kit while on the video call to ensure they are using a new test each time
- Participants will be asked to write down the participants id, test number, date, and time on the test kit
- Participants will take a picture, including participant id, test number, date, and time for verifying the final results and provide the final results and picture to the research

staff before ending the call (approximately 10-minute processing time) All participant will need to provide a saliva sample at the in-person baseline and the Week 12 visits and at remote video calls (Week 6, Week 8, and Week 10).

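### The n=80 rationale uses a standard-deviation rule to claim sufficiency for preliminary effectiveness, which it does not support for a binary primary outcome, and it misnames the randomised components

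*Combined protocol and SAP*

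**What the plan says.** Section 4.A plans 80 participants, "with n=20 for each arm". The justification in 4.A.2 is a rule of thumb, "a minimum sample size of 12 subjects per treatment arm or a total sample size of 70", whose stated purpose is "in order to reduce the imprecision around the estimate of the standard deviation for a pilot trial". The next sentence draws its conclusion directly from that rule: "the sample size of 80 for this study would be sufficient to assess the preliminary effectiveness of financial and social incentives". The same sentence adds feasibility and the ability to scale up.

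The primary outcome in section 12.B is biochemically verified abstinence ("negative results- will be cut-off < 30 ng/mL"), "measured by saliva cotinine samples at the Week 12 visit". Each participant is therefore either negative or not. Section 2 hypothesises better abstinence in the Combined arm than in the Media literacy and Financial incentive arms. Section 12.E compares groups by chi-square test for categorical variables and by adjusted regression, with significance at p<0.05.

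Under section 12.B, eligible people "will be randomized (1:1:1:1) to receive one of the following interventions": text messaging alone, text messaging with media literacy, text messaging with a financial incentive, or text messaging with both.

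**The concern.** The conclusion in 4.A.2 does not follow from its premise. A rule for estimating a standard deviation concerns a continuous measurement. For a binary outcome the variance is p(1−p), fixed by the proportion itself, so there is no separate standard deviation to pin down. Meeting the rule therefore gives no information on how well abstinence will be estimated. The documents supply nothing else in its place: no expected abstinence rate, effect size, power, target interval width or allowance for loss to follow-up.

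The sentence also does not describe the trial as randomised. Media literacy and financial incentive are what differ between arms; social incentives are not assigned by randomisation.

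At stake is how the abstinence results are read. The plan tells the reader that the sample is sufficient for preliminary effectiveness and then applies p<0.05. Nothing in it says how wide the uncertainty on each arm contrast will be.

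**Working it through.** **Inputs from the documents.** Four arms of 20, total 80 (4.A); the rule of 12 per arm or 70 in total (4.A.2); a binary primary outcome at Week 12 (12.B); abstinence contrasts of Combined v each single-component arm (section 2); significance at p<0.05 (12.E).

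**Assumptions, because the documents are silent.** Two-sided 95% intervals; abstinence of 10% to 50%, equal in the two arms compared; and, as an illustration of attrition, 20% loss, leaving 16 per arm.

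**The plan's own figure.** 4 × 20 = 80, which exceeds both thresholds (4 × 12 = 48, and 70). The rule is met on its own terms. The plan states no power or precision figure that could be reproduced.

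**Two-arm contrast, 20 v 20.** Half-width = 1.96 × √(2p(1−p)/20):

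- p = 10%: 1.96 × √(2 × 0.09/20) = 18.6 points
- p = 20%: 1.96 × √(2 × 0.16/20) = 24.8 points
- p = 30%: 1.96 × √(2 × 0.21/20) = 28.4 points
- p = 50%: 1.96 × √(2 × 0.25/20) = 31.0 points

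Unequal rates give similar values: 21.9 points for 10% v 20%, and 27.7 for 20% v 40%. Newcombe intervals, which behave better in small samples, have half-widths of 21.4 points at 2/20 v 2/20, 24.7 at 4/20 v 4/20 and 28.4 at 10/20 v 10/20. The conclusion does not depend on the Wald formula.

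**With 16 per arm analysed.** At p = 20%: 1.96 × √(2 × 0.16/16) = 27.7 points.

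**What n=80 does give for feasibility.** Half-width of one proportion = 1.96 × √(p(1−p)/n):

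- All 80 participants: 8.8 points at 20%, 11.0 at 50%
- Lesson completion, which applies only to the 40 in the Media literacy and Combined arms: 1.96 × √(0.16/40) = 12.4 points at 20%; 1.96 × √(0.25/40) = 15.5 at 50%

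**Components.** Section 4.A.2 names financial and social incentives. The arms in section 12.B vary media literacy (two arms) and financial incentive (two arms). Only financial incentive appears in both lists.

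**The case against.** The strongest defence is that this is a pilot. Section 4.A.2 opens by saying so, claims only *preliminary* effectiveness, and covers feasibility as well. A pilot need not be powered. That stands, and it rules out several stronger readings.

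- *The trial is underpowered.* A reader might infer this: for 20% v 40% with 20 per arm, power is about 28% by normal approximation, or 19% by Fisher's exact test. But the documents claim no power and no definitive test. The fault is a justification that does not match the outcome and gives no precision.
- *Every arm contrast carries ±25 points.* That figure needs about 20% abstinence in both arms, a rate the documents never give. At 5% the half-width is ±13.5, at 50% ±31.0.
- *Scale-up will be decided on p<0.05 for abstinence.* No section says so. The significance level in 12.E is a general statement that plausibly covers abstinence but does not name it.
- *The standard-deviation rule is irrelevant to the trial.* Section 12.B lists a dependence index and a media literacy scale as secondary outcomes, and 12.E plans ANOVA for continuous variables. The rule may inform those. Its source is not available here, so whether it is quoted correctly was not judged.
- *The trial has no social element.* The text programme given to every arm draws on social norms and support. The narrower statement holds: social support is not a randomised component.
- *Pooling arms 40 v 40 rescues abstinence.* It would give ±17.5 points at 20%, but section 2 pools the incentive arms for engagement, not abstinence. Reading pooled margins as component effects would also assume no interaction.

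None of this makes the inference in 4.A.2 valid for the binary primary outcome.

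**Conclusion.** The concern holds in a limited form. The rule cited in 4.A.2 does not support the statement that 80 is sufficient to assess preliminary effectiveness on cotinine-verified abstinence, and the sentence misstates which components are tested. With 20 per arm, a contrast such as Combined v Media literacy or Combined v Financial incentive would carry a 95% half-width of about ±19 to ±31 points, and about ±28 at 20% abstinence if 16 per arm are analysed. These figures rest on assumed abstinence of 10% to 50% in both arms, two-sided intervals and, in the last case, an assumed 20% loss. The size of the trial is not itself the fault. What needs correcting is the stated justification and the absence of any precision statement for the primary outcome.

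**What to change.** Keep n=80 and replace the sufficiency sentence in 4.A.2 with text that:

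- gives the precision of a two-arm abstinence contrast as about ±19 to ±31 points, with the 10% to 50% rates labelled as an assumption and the effect of attrition shown;
- gives about ±9 to ±11 points for feasibility proportions over all 80, and about ±12 to ±15.5 for lesson completion in the 40 assigned to lessons (rates of 20% to 50%);
- states that the trial is not sized to test differences in abstinence;
- names media literacy and financial incentive as the components;
- if the standard-deviation rule is kept, ties it to the secondary scale scores.

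In section 12.E, add that abstinence contrasts will be reported as estimates with 95% confidence intervals, and that p<0.05 on abstinence will not be taken as evidence for or against effectiveness.

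The cost is one rewritten paragraph and one added sentence. Enrolment and arms do not change. The downside is that the stated claim becomes less favourable.

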For quality improvement and future modification and adoption of the multi-component vaping cessation program, we will conduct an exit interview (n=8-12; n=2-3 from each arm based on first available participants) via a video call, with participants to identify the feasibility, facilitators, and barriers of implementing the proposed interventions. Participant who have completed the end-of-study assessment will be contacted by research staff for their willingness to participate in the exit interview. The interview will take place after the Week 12 visit based on participant's availability via a zoom meeting. Therefore, the total participating time in the study is roughly 14-16 weeks. The interview will be audio-recorded and transcribed in order to produce an accurate transcript of the discussion. Each participant in the exit interview will receive a \$25.00 giftcard. The interview will last less than 30 minutes.

Participant enrollment process

Interested potential participants will complete an online screen survey (RedCap link embedded in the recruitment email; and less than 5 minutes to complete), to determine their eligibility based on the inclusion and exclusion criteria. Once potential participants have been deemed as eligible through screening questions, participants will be asked if they would like to participate. If they agree, they will be asked to indicated the times and days that participants would be available to attend the in-person session to complete the informed consent, intake process, including providing saliva sample, urine sample (only for 20 participants who volunteer to be in the biomarker measurement group), and completing the baseline survey (less than 20 minutes to complete), consisting of demographic information, vaping history, vaping experience/behavior, exposure to Tobacco Marketing and Marketing Influences, social efficacy, UPPS impulsive behavior scale, money choice question, and nicotine dependence index (Penn State Cigarette Dependence Index). After completing all the tasks at the baseline session, a randomization algorithm will be utilized to decide which interventions (*Active control, Media literacy, financial incentive, and Combined*) that a participant will be assigned to.

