Upon randomization, research staff will review the intervention component based on the intervention group that they are assigned to with the participants and provide instruction and materials for the followup sessions.

D. Identify:

1. All procedures, interventions, evaluations and tests performed solely for research purposes (eg, administration of an investigational drug or a new psychological assessment instrument; randomization)

- We will administer a set of educational lessons about vaping cessation that discuss what e-cigarettes are and how they work, how nicotine and nicotine addiction affects the brain and behavior, how to prepare to quit vaping, developing a quit plan and how to deal with cravings and relapse.
- We will facilitate participants to download and enroll in the evidence-based vaping cessation support text-messaging program (This is quitting, <https://truthinitiative.org/thisisquitting>)
- We will administer monetary incentives based on engagement (submitting saliva samples at Week 6, Week 8, and Week 10), and the efforts with vaping cessation (abstinence results).
- We will evaluate nicotine levels in the body for program efficacy via 5 saliva sample (2 at in-person baseline and Week 12 visits and 3 at check-in video calls at Week 6, Week 8, and Week 10); and two urine cotinine tests for biomarker of toxic exposure (only for 20 participants in the biomarker measurement group) at in-person baseline and Week 12 visits)
- We will administer a set of screening questions, baseline/end-study surveys, and vaping-related symptom questionnaires (e.g., wheezing and related respiratory symptoms)-only for 20 participants assigned to the biomarker measurement group).
- For quality improvement and future modification and adoption of vaping cessation programs, we will conduct an exit interview with participants (n=8-12; n=2-3 from each arm based on first available participants) who have completed the final study visit through a video call. We will assess the feasibility, facilitators, and barriers to participation and engagement in the study's vaping cessation interventions.

2. All procedures, interventions, evaluations and tests performed for clinical indication but more frequently than they would be if the subject was not participating in the research (eg, extra blood tests; additional radiology exams)

None.

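### Exit interviews on barriers to participation are open only to Week 12 completers, so reasons for non-retention go uncollected

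*Combined protocol and SAP*

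**What the plan says.** Section 12.B (research plan) gives the number and selection rule as "n=8-12; n=2-3 from each arm based on first available participants". The purpose stated there is "to identify the feasibility, facilitators, and barriers of implementing the proposed interventions". The pool is defined in one sentence: "Participant who have completed the end-of-study assessment will be contacted by research staff for their willingness to participate in the exit interview". On timing: "The interview will take place after the Week 12 visit based on participant's availability via a zoom meeting".

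Section 12.D.1 (research-only procedures) repeats the restriction, describing interviewees as those "who have completed the final study visit through a video call", and words the purpose more widely: "We will assess the feasibility, facilitators, and barriers to participation and engagement in the study's vaping cessation interventions".

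The two sections agree on who is interviewed. Feasibility is Aim 1 in the protocol summary, and Section 6.A names retention, alongside reach and engagement, among the things the support is meant to improve.

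**The concern.** An interview meant to learn what stops people taking part draws only on people who stayed to the end. Those who left before Week 12, or did not come to that visit, are best placed to explain non-retention, and the rule leaves them out. Section 18.E lists poor retention among the possible reasons for discontinuing the trial, so the team could find itself knowing that people were lost without knowing why. Changes made for a larger trial would then rest on what completers found difficult.

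A second, weaker worry is the order of selection. Taking the first available completers gives no assurance that less engaged completers are heard.

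**Working it through.** **Inputs from the documents.** 80 participants in 4 arms of 20 (Section 4.A); 2-3 interviews per arm, first available among Week 12 completers (Sections 12.B and 12.D.1).

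**Assumed inputs.** The documents give neither attrition before Week 12 (*a*) nor the share of low engagers among those interviewed (*q*). Ranges are used: *a* = 10-40%, *q* = 5-50%.

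**Step 1: the plan's own figure.** 4 × 2 = 8 and 4 × 3 = 12, as stated. This is 8/80 = 10% to 12/80 = 15% of participants.

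**Step 2: non-completers.** Under the written rule their chance of interview is 0 at any attrition rate. For comparison, suppose *n* = 8-12 people were drawn at random from all 80. The expected number of non-completers is *n* × *a*, and P(at least one) = 1 − (1 − *a*)^*n*. For example, at *a* = 20%: 1 − 0.8^8 = 0.832 and 1 − 0.8^12 = 0.931.

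| Assumed attrition | Non-completers of 80 | Expected in 8-12 random interviews | P(at least one), random draw | P(at least one), written rule |
|---|---|---|---|---|
| 10% | 8 | 0.8-1.2 | 57-72% | 0 |
| 20% | 16 | 1.6-2.4 | 83-93% | 0 |
| 30% | 24 | 2.4-3.6 | 94-99% | 0 |
| 40% | 32 | 3.2-4.8 | 98-99.8% | 0 |

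The formula treats draws as independent. Drawing without replacement from 80 would make the random-draw probabilities slightly higher.

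**Step 3: low engagers who attend Week 12.** They are eligible. With the same formula and *q* as their share among those drawn:

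| Assumed share *q* | At least one in 8-12 interviews | At least one within an arm (2-3 interviews) |
|---|---|---|
| 5% | 34-46% | 10-14% |
| 10% | 57-72% | 19-27% |
| 20% | 83-93% | 36-49% |
| 30% | 94-99% | 51-66% |
| 50% | over 99% | 75-88% |

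So low engagers may well appear somewhere in the interviews, but often not in every arm. If first-available selection favours the more engaged, the effective *q* is lower than their share among all completers.

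**Step 4: is the gap filled elsewhere?**

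- The end-of-study survey is completed at the in-person Week 12 visit (Section 12.B, Measurement), so it reaches attenders only.
- Staff check-ins take place on the video calls (Section 18.A), so they too reach attenders only.
- Weekly reports on participation, engagement, retention and flow, and monthly review of adverse events and receipt of components (Sections 18.A and 18.B), show how many were lost. They are not described as recording why.
- Participants leave at their own request (Section 18.D); no reason is asked for.
- Self-reported pregnancy leads to disenrollment (Section 11.B), and adverse events may be volunteered (Sections 18.A and 18.B). These could reveal a particular reason in passing, but neither is an inquiry into why someone did not return.

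**The case against.** The strongest reply is that the restriction is narrower than it looks. The only condition is completing the end-of-study assessment. A reader might infer that people who missed calls or skipped lessons are also shut out, and hence that barriers behind disengagement cannot be seen at all. The documents do not support that. The engagement outcome in Section 12.B is lessons completed and remote samples submitted, and neither is a condition for interview. Section 18.D keeps people in the study whatever they leave undone, and Section 23.A pays every arm $25 for attending Week 12 regardless of earlier engagement. Someone who skipped every lesson and call can attend and be interviewed. This part of the reply stands in full.

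A reader might also infer that first available means earliest enrolled or most engaged, or that the feasibility conclusion is biased toward acceptability in every arm. Neither is shown. The documents do not define first available beyond scheduling and give no data linking availability to engagement. The interviews are introduced as serving quality improvement and future modification, while feasibility also draws on engagement outcomes and on retention and flow reports that are not limited to interviewees. Dropout will be counted.

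Finally, a small, openly stated convenience sample is common in a qualitative component, and most completers will not be interviewed either. That is true, but it does not answer the remaining point: non-completers are left out by rule rather than by chance, and their reasons are sought nowhere else.

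**Conclusion.** The point holds as a limited one. Participants who miss Week 12 cannot be interviewed, and no other procedure asks for their reasons, although Section 12.D.1 gives the purpose as including barriers to participation and engagement. The interviews therefore cannot inform why participants were not retained. Low engagers who do attend Week 12 are eligible and at most under-represented.

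The zero chance for non-completers follows from the text and needs no assumption. The number affected does: 8 to 32 of 80 for attrition of 10-40%, a range chosen for illustration. The primary outcome, verified abstinence at Week 12, and its analysis are not touched. This is a cheap improvement to the Aim 1 evidence, not a flaw that threatens the trial.

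**What to change.** In Sections 12.B and 12.D.1, keep 8-12 interviews at 2-3 per arm, but reserve one slot per arm, offered in this order:

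1. a participant who missed the Week 12 visit and has not withdrawn consent;
2. a completer who missed at least one remote sample or, in the *Media literacy* and *Combined* arms, at least one lesson;
3. any other completer.

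The order matters. If the first two groups were merged, Week 12 attenders, who are already eligible, could fill every reserved slot. The protocol should also say how long a slot is held before it passes down the list. Four reserved slots (4 × 1) are 4/12 = 33% to 4/8 = 50% of the interviews.

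Report how many interviewees were non-completers. If there were none, state that the interview findings describe completers only.

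The interviews are already held by video, and Section 15.B records telephone and e-mail details with follow-up as a stated reason, so contact is practicable. No extra interviews or gift cards are needed. The costs are a few more contact attempts, some waiting while slots are held, reserved slots that may go unfilled, and a small protocol amendment with any matching change to the consent wording. People who have withdrawn consent would still not be heard.
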